**vi. Oculus Keratograph 5M, Part 2**

This instrument was also used for imaging sodium fluorescein and Lissamine green staining, graded using the Oxford scale (from 0, absent to 5, severe) for the overall cornea and bulbar conjunctiva [10]. For each participant, a fluorescein sodium impregnated dry strip (Bio Fluoro, Bio-Tech Vision Care, Gujarat India) was moistened with a drop of saline solution (sodium chloride 0.9%), and the excess fluid shaken off, before applying on the lower temporal palpebral conjunctiva after slightly everting the lower eyelid. The same was done with a lissamine green impregnated dry strip (Contacare Ophthalmics and Diagnostics, Gujarat, India), but with the excess fluid allowed to fully coat the whole strip, before a large droplet was instilled in the same manner. Imaging was conducted following this using the in-built blue light and yellow filter, and then the white light for lissamine green staining. Following upper and lower lid eversion, lid wiper epitheliopathy was also assessed by grading the width (0: < 25 %; 1: 25 to 50 %; 2: 50 to 75 %; 3: > 75 %) and length (0: < 2 mm; 1: 2 to 4 mm; 2: 5 to 9 mm; 3: > 10 mm) of the staining [11], and an average of the width and length grading taken as the lid wiper epitheliopathy grading for each of the upper and lower eyelid. Meibography of the upper and lower lids were performed and graded using the meiboscale for the percentage area of gland loss or atrophy compared to the whole tarsal area (0: around 0%; 1:  $\leq 25\%$ ; 2: 26 to 50%; 3: 51 to 75%; 4:  $> 75\%$ ) [12].

**vii. In-vivo corneal confocal microscopy**

The Heidelberg Retinal Tomograph III with Rostock Corneal Module (Heidelberg Engineering GmbH, Heidelberg, Germany) was used to image the sub-basal nerve plexus of the central cornea and inferior whorl. One drop of anaesthetic eyedrop (proxymethacaine hydrochloride 0.5% minims, Bausch & Lomb, Surrey, United Kingdom) used routinely in clinical practice was administered in both eyes for comfort and to minimise blinking for image capturing. Analyses of the total corneal nerve length (in  $\text{mm/mm}^2$ ) using a semi-automated method in NeuronJ, a plugin of Image J (National Institutes of Health, Maryland, United States of America), and density of immune cells [ $\text{cells/mm}^2$  of putative epithelial T cells (small, immune cells with no visible dendrites) and of dendritic cells (larger cells with dendritiform shape and apparent dendrites)] [13] using the Cell Counter plugin within ImageJ, from the central corneal (4 images randomly selected) were conducted. Total inferior whorl nerve length was also measured using NeuronJ from 1 image of the inferior whorl, an anatomical landmark where the sub-basal corneal nerves traverse towards 1 to 2 mm inferonasal to the central cornea.

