#### 1. Light-based treatment protocol

The Eye-light unit (Espansione Group Ltd, Funo, Italy) was used to deliver the light-based therapies. Prior to the intense pulsed light therapy (IPL), the highest meiboscore of either eyelid and the Fitzpatrick skin grading was inputted into the unit system. This automatically calibrated the optical radiance output of the IPL. Table 1 details the exact output for each combination of settings.

**Table 1.** Optical radiance output of the intense pulsed light (IPL) therapy of the Eye-light unit (Espansione Group Ltd, Funo, Italy) according to inputted grading from the meiboscale and Fitzpatrick skin grading.

Pult Meiboscale	Fitzpatrick skin grading	Optical radiance output (J)
1	1	59
	2	59
	3	59
	4	59
2	1	60
	2	62
	3	62
	4	60
3	1	62
	2	66
	3	66
	4	64
4	1	65
	2	69
	3	69
	4	67

Figure 1 demonstrates the light-based treatment administration protocol used in this clinical trial for four treatment sessions.

**Figure 1.** Intense pulsed light (IPL) protocol with (A) sequential placements of treatment cartridge for the five different regions involved, and (B) sham IPL placement of a disconnected empty cartridge along the same five different regions on the contralateral side but with the working IPL cartridge pointed away from the patient's face to simulate a pulse. Low-level light therapy (LLLT) was then administered for 15 minutes (C) with placement of the mask consisting of a series of red light-emitting diodes (LEDs). These were conducted with the Eye-light unit (Espansione Group Ltd, Funo, Italy).

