## Statistical Analysis

Two-factor repeated measures analysis of variance (ANOVA) was used for statistical analysis to assess changes over time across the multiple visits between each treatment group. One-way repeated measures ANOVA was used to assess changes over time for overall measures including OSDI scores, DEQ-5 scores, visual acuity, and blink rate. The Greenhouse-Geisser correction was applied to the one-way and two-factor repeated measures ANOVA results to adjust for the lack of sphericity. Paired t-test for normally distributed data or Wilcoxon signed-rank test for non-normally distributed data was used to assess differences between the two treatment modalities within the same visit.

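### Inferior whorl nerve length comes from one image with no stated rule for choosing it; averaging up to three centred frames would gain some precision, by an amount the documents do not fix

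*Combined protocol and SAP*

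**What the plan says.** Section vii, In-vivo corneal confocal microscopy, gives two nerve-length measures.

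- **Central cornea:** nerve length and immune cell density are taken "from the central corneal (4 images randomly selected) were conducted". Nerve length is traced "using a semi-automated method in NeuronJ, a plugin of Image J".
- **Inferior whorl:** "Total inferior whorl nerve length was also measured using NeuronJ from 1 image of the inferior whorl". The sentence goes on to describe the whorl as "an anatomical landmark where the sub-basal corneal nerves traverse towards 1 to 2 mm inferonasal to the central cornea".

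The section does not say how the whorl frame is chosen, centred or focused. It does not say whether more than one usable whorl frame was captured, or whether the person choosing and tracing the frame was masked to side. That the single image is per eye and per visit is the natural reading, not stated text.

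Table 2 schedules confocal microscopy at Visits 1, 5 and 6. The treatments are compared within a person: Figure 1 describes "sham IPL placement of a disconnected empty cartridge along the same five different regions on the contralateral side". Under Statistical Analysis, a paired t-test or Wilcoxon signed-rank test "was used to assess differences between the two treatment modalities within the same visit". For the time course, "Two-factor repeated measures analysis of variance (ANOVA) was used for statistical analysis to assess changes over time across the multiple visits between each treatment group". Whorl length is not named there, but as a per-eye measure it falls under these two analyses. No outcome is named as primary.

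**The concern.** The total length traced in one frame depends on where the whorl sits in the field and on the depth of focus, as well as on the nerves. If the frame is aimed or focused a little differently on the other eye, or at Visit 5 or 6, the length can change when the nerves have not. With a single frame, none of that error is averaged out. A side difference at one visit carries the error of two single frames. A between-side difference in change from Visit 1 carries the error of four.

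Elsewhere the plan does use replicates. Section iii averages three measures for tear meniscus height and three for non-invasive break-up time, and section vii uses four images for the central cornea. What is at stake is the ability to detect a real whorl difference and to interpret a null one.

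**Working it through.** There is no plan figure to reproduce. The documents give no standard deviation, repeatability or frame-to-frame variance for whorl length. What follows is a range under assumed inputs.

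**From the documents:** 1 whorl image (section vii); 3 confocal visits (Table 2); two sides per person (Figure 1).

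**Assumed:**
- Set the variance of the side difference with one frame per eye to 1.
- *f* is the share of that variance due to frame placement, focus and tracing. Values: 0.10, 0.30, 0.50.
- *r* is the correlation of these errors between frames of the same whorl at the same visit. Values: 0, 0.5, 0.8.
- *m* = 3 frames are averaged, all of equal quality.

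**Formulas:**
- Variance after averaging: V = (1 − f) + f × [r + (1 − r)/m]
- Cut in standard error: 1 − √V
- Equivalent gain in participants: 1/V − 1

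**The two ends of the range:**
- f = 0.10, r = 0.8: V = 0.90 + 0.10 × (0.8 + 0.2/3) = 0.987. √V = 0.993, a cut of 0.7%. 1/0.987 − 1 is about 1%.
- f = 0.50, r = 0: V = 0.50 + 0.50/3 = 0.667. √V = 0.816, a cut of 18.4%. 1/0.667 − 1 = 50%.

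**All combinations with three frames.** The last column shows what an assumed 80% power with one frame (two-sided 0.05, normal approximation) would become.

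| f | r | V | Cut in SE | Equivalent gain in n | Power from 80% |
|---|---|---|---|---|---|
| 0.10 | 0 | 0.933 | 3.4% | 7% | 82.6% |
| 0.10 | 0.5 | 0.967 | 1.7% | 3% | 81.3% |
| 0.10 | 0.8 | 0.987 | 0.7% | 1% | 80.5% |
| 0.30 | 0 | 0.800 | 10.6% | 25% | 87.9% |
| 0.30 | 0.5 | 0.900 | 5.1% | 11% | 84.0% |
| 0.30 | 0.8 | 0.960 | 2.0% | 4% | 81.6% |
| 0.50 | 0 | 0.667 | 18.4% | 50% | 92.9% |
| 0.50 | 0.5 | 0.833 | 8.7% | 20% | 86.6% |
| 0.50 | 0.8 | 0.933 | 3.4% | 7% | 82.6% |

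Frames of one landmark overlap and show much the same nerves, and frames from one pass may also share depth and placement. Both point to a higher *r*, and so to the lower part of the table.

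**Tracing load:** 2 extra frames × 2 eyes × 3 visits = 12 more tracings per participant at most.

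**The case against.** The strongest objection is that one image versus four is a reasonable choice. The central images are random fields from a region for which the section names no landmark, so several are needed to sample it. The whorl is one located structure. A reader might infer from the two counts that the plan contradicts itself. It does not, because the same sentence that gives the single image also gives the landmark. What the landmark leaves open is where the structure sits in the frame and at what depth, and no rule covers either.

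Second, much of the placement error could be removed by a centring rule alone, with one frame. This stands. Once frames are centred, *f* falls and averaging adds less, which is why the fix puts the rule first.

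Third, a reader might infer that averaging needs nothing but more tracing. The documents do not say that spare usable whorl frames were captured. The text is in the past tense, so if none were kept, the change may not be possible for visits already completed.

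Fourth, a reader might infer that frame error cannot be assessed at all with one image. That goes too far: retracing, or repeat imaging in a subset, would give a repeatability figure. Retracing alone would cover only the tracing part.

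Finally, the gain may be negligible, since at f = 0.10 and r = 0.8 it is 0.7%. This stands as a limit on the size of the point. It does not show that one frame is as good as an average of comparable frames.

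**Conclusion.** The point holds as a minor matter of precision. Whorl length rests on one image chosen by no stated rule, and averaging comparable frames would reduce its random error unless the errors were fully correlated. With three frames the cut in standard error is about 0.7% to 18% (about 1% to 50% more participants) over f = 10-50% and r = 0-0.8. The lower part is more plausible. Both *f* and *r* are assumptions, and the documents cannot narrow them.

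A reader might go on to infer that the side comparison is biased. The documents do not support that: frame error unrelated to side widens the paired difference but does not shift it. That conclusion assumes frame choice and tracing do not depend on side, and the section is silent on masking for this step. Nor do the documents show that the noise is large. Whorl length is one of many outcomes, none named as primary.

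**What to change.** In section vii, In-vivo corneal confocal microscopy:

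1. State the rule by which a whorl frame qualifies: how it is centred and at what focus, applied in the same way to both eyes and at every visit.
2. Trace up to three qualifying frames per eye and visit, from separate passes over the whorl where available, and analyse their mean.
3. Where only one usable frame exists, use it and say so.
4. Report between-frame repeatability, so that a null result can be read against the measurement error.

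The cost is up to 12 more semi-automated tracings per participant in software already in use and, if spare frames were not captured, slightly longer image capture. No new procedure or staff is needed. If imaging is finished and no spare frames were kept, what remains is to report how the single frame was chosen and to describe whorl length as resting on one frame.

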## Statistical Analysis

Two-factor repeated measures analysis of variance (ANOVA) was used for statistical analysis to assess changes over time across the multiple visits between each treatment group. One-way repeated measures ANOVA was used to assess changes over time for overall measures including OSDI scores, DEQ-5 scores, visual acuity, and blink rate. The Greenhouse-Geisser correction was applied to the one-way and two-factor repeated measures ANOVA results to adjust for the lack of sphericity. Paired t-test for normally distributed data or Wilcoxon signed-rank test for non-normally distributed data was used to assess differences between the two treatment modalities within the same visit.

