## 2. Ocular assessment schedules and details

The study was structured into multiple visits and all conducted at the Aston Dry Eye Clinic in Aston University, Birmingham, United Kingdom. Each visit lasted for about 1.5 hours, with the sequence of assessments detailed in Table 2:

- Visit 1: Screening ± First treatment session
- Visit 2 (2 to 3 weeks after Visit 1): Second treatment session
- Visit 3 (2 to 3 weeks after Visit 2): Third treatment session
- Visit 4 (2 to 3 weeks after Visit 3): Fourth and final treatment session
- Visit 5 (2 weeks after visit 4): First follow-up
- Visit 6 (3 months after visit 4): Second and final follow-up

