**Table 2. The sequence of assessments for each visit**

Procedures	Visits					
	1	2	3	4	5	6
Screening with inclusion and exclusion criteria	✓					
OSDI, DEQ5 and adapted SANDE questionnaires	✓	✓	✓	✓	✓	✓
General medical and ocular history, and lifestyle questions	✓	✓	✓	✓	✓	✓
Visual acuity assessment	✓	✓	✓	✓	✓	✓
Oculus Keratograph 5M, Part 1	✓	✓	✓	✓	✓	✓

 
- Number of total and partial blinks in 30 s
 
- Tear meniscus height
 
- Non-invasive tear break up time
 
- Lipid layer pattern
 
- Bulbar and limbal hyperaemia grading
 
						
Laser Doppler flowmetry and multimodal spectroscopy at central lower eyelids	✓				✓	✓
Slit lamp biomicroscopy	✓	✓	✓	✓	✓	✓

 
- Telangiectasia grading
 
						

Procedures	Visits					
	1	2	3	4	5	6

 
- Number of blocked or capped Meibomian gland orifices
 
- Demodex detection (2 lashes randomly chosen on either lid and assessed with lateral traction method)
 
- Meibomian gland expression with Korb expressor
 
						
Oculus Keratograph 5M, Part 2	✓	✓	✓	✓	✓	✓

 
- Fluorescein sodium and lissamine green staining grading on ocular surface and lid wiper epitheliopathy
 
						
Meibography	✓				✓	✓
In-vivo corneal confocal microscopy	✓				✓	✓

The following provides further details the instrumentation or procedures involved:

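### No missing-data method is given for the repeated-measures ANOVAs; a mixed model on all attended visits should estimate the follow-up changes, with the planned ANOVA kept as the all-visit test

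*Combined protocol and SAP*

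**What the plan says.** The Statistical Analysis section is one short paragraph. For treatment by time it states "Two-factor repeated measures analysis of variance (ANOVA) was used for statistical analysis". For OSDI, DEQ-5, visual acuity and blink rate it states "One-way repeated measures ANOVA was used to assess changes over time for overall measures". The only adjustment to these models is for sphericity: "The Greenhouse-Geisser correction was applied to the one-way and two-factor repeated measures ANOVA results to adjust for the lack of sphericity". A paired t-test or Wilcoxon signed-rank test "was used to assess differences between the two treatment modalities within the same visit".

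The schedule in section 2 has six visits, each treatment visit timed from the one before ("Visit 2 (2 to 3 weeks after Visit 1): Second treatment session") and ending with "Visit 6 (3 months after visit 4): Second and final follow-up". Table 2 places most outcomes at all six visits. Three groups are measured at Visits 1, 5 and 6 only: the row "Laser Doppler flowmetry and multimodal spectroscopy at central lower eyelids", meibography and confocal microscopy. The treatment comparison is within person, with "sham IPL placement of a disconnected empty cartridge along the same five different regions on the contralateral side" (Figure 1 legend).

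The available text does not mention missed visits, withdrawal, imputation, an analysis set or a mixed model. One passage was removed before review and could not be checked.

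**The concern.** Classical repeated-measures ANOVA needs a value at every level of the within-person factor. Greenhouse-Geisser adjusts the degrees of freedom for unequal variances of differences; it does nothing for absent values. Unless values are imputed, which the plan does not mention, a participant with one gap leaves that outcome's ANOVA altogether, and both sides go together. The paired tests keep that participant at every visit attended, so the two analyses could describe different people without the reader being told.

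At stake are precision for change over time, from data already collected, and possibly bias if those who stay differ from those who leave.

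**Working it through.** **Inputs.** From the documents: six scheduled visits for most outcomes and three for the groups named above. The documents give no sample size, power, effect size or attendance, so there is no plan figure to reproduce. Every rate, effect and n below is an assumption.

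**1. Does one gap matter?** Software check with 20 people × 2 sides × 6 visits = 240 rows. One person misses one visit, leaving 240 − 2 = 238. A standard repeated-measures ANOVA routine stopped because the data were unbalanced. Removing that person discards the other 12 − 2 = 10 observed rows. A mixed model used all 238 rows and all 20 people.

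**2. Share kept by the ANOVA.** Visit 1 attended; each later scheduled visit missed independently with probability m; share = (1 − m)^k.

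| m | six-visit outcomes, k = 5 | three-visit outcomes, k = 2 |
|---|---|---|
| 2% | 0.98^5 = 90% | 0.98^2 = 96% |
| 5% | 0.95^5 = 77% | 0.95^2 = 90% |
| 10% | 0.90^5 = 59% | 0.90^2 = 81% |

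If only Visits 5 and 6 can be missed, the k = 2 column applies to six-visit outcomes too. With permanent dropout of 5% / 10% / 20% in total, 95% / 90% / 80% remain.

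**3. Power, like for like.** Test: side difference at Visits 5 and 6 jointly against Visit 1 (2 df). Assumed: n = 30, both changes equal to 0.5 SD of change, equal correlation 0.5 between visits (so the two changes also correlate 0.5), two-sided 5%. On completers this is Hotelling's T-squared:
- squared distance = 0.5² × 2 / (1 + 0.5) = 0.333
- noncentrality = 30 × 0.333 = 10, on F with 2 and 28 df, giving 77% with full attendance
- with loss, the power is averaged over the binomial number retained.

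The mixed-model figures come from 800 simulated trials per case (Monte Carlo SE about 1.5 points).

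| Loss | completers, same 2-df test | mixed model, all attended visits | gain, points |
|---|---|---|---|
| none | 77% | 77% | 0 |
| 10% total dropout | 71% | 74% | 3 |
| 20% total dropout | 65% | 72% | 7 |
| 5% missed at each of Visits 5 and 6 | 72% | 74% | 2 |
| 10% missed at each of Visits 5 and 6 | 66% | 73% | 7 |

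The gains of 2 and 3 points are no more than about two Monte Carlo standard errors.

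**4. Bias.** Simulated dropout of 10% / 20%:
- Change over time, true value −0.40 SD: completers give −0.44 / −0.48 if those not improving leave, but −0.39 / −0.37 if dropout follows the previous score.
- Side difference, true value −0.30: completers stay at −0.30 unless dropout follows the side difference itself, then −0.33 / −0.36.
- In a separate simulation where dropout followed the previous side difference (true value 0.40, about 77% completing), completers gave 0.54 and a likelihood estimate on all attended visits gave 0.38 to 0.39.

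**5. Error control of the replacement.** Complete data, n = 30, no effect, side-difference correlation decaying with half-life 4 / 8 / 16 weeks. A Visit 6 minus Visit 1 contrast on a pooled variance rejected in 11.7% / 14.8% / 17.2% of runs; on its own variance, in 5.4% / 4.9% / 5.0%.

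**The case against.** The strongest reply is that the loss may be nil. No attendance is stated, and with complete attendance the ANOVA discards nothing. Visits 2 to 4 deliver treatment and each is timed from the previous visit, so a missed session may shift the schedule rather than leave a gap. Both points stand. They make dropout, or gaps at Visits 5 and 6, the plausible patterns, and the 59% share an extreme case.

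A reader might infer a larger benefit by setting the mixed model's 2-df test (74% / 72% at 10% / 20% dropout) against the planned all-visit ANOVA on completers (67% / 59%), an apparent gain of 7 / 13 points. That comparison also changes the hypothesis from all visits to two, under an assumed effect that favours the second. Handling of missing visits alone accounts for about 3 / 7. Nor is there a full-attendance advantage to claim if correlation decays over time: on complete data the unstructured model's test is Hotelling's, with exact power of 73-80% depending on how the effect is scaled, against about 80% for the ANOVA.

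A reader might also infer that the all-visit test should be replaced. It should not. If the side difference builds during treatment, holds to Visit 5 and fades by Visit 6, the ANOVA has 85% power and the 2-df test 78% at full attendance. A 5-df test from the unstructured model is itself weaker than the ANOVA there (70% against 75% for the effect in step 3, rising to Visit 5 and then held). The plan's purpose covers both short- and long-term change.

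Finally, many outcomes are coarse grades, and the simulations used generic continuous scores. That limitation stands.

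**Conclusion.** The gap is real: the only change-over-time analysis has no rule for missed visits and, as ordinarily run, drops incomplete participants while the paired tests keep them. A better method is available at low cost. Its benefit is zero with full attendance and, under the assumptions in step 3, roughly 3 and 7 power points at 10% and 20% dropout.

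The documents do not support the inference that participants were in fact dropped, or that the results are biased. Completer bias in change over time may be near zero or go either way. For the treatment contrast, none is shown unless dropout follows the difference between sides. This is a worthwhile improvement, held with moderate confidence because sample size and attendance are unknown.

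**What to change.** 1. Estimate changes from Visit 1 to Visits 5 and 6 with a REML linear mixed model on all attended visits: visit as fixed effect, unstructured visit covariance, Kenward-Roger degrees of freedom.
2. For person-level outcomes (OSDI, DEQ-5, visual acuity, blink rate), fit it to the score. For per-eye outcomes, fit it to the within-person side difference and, separately, to the mean of both sides.
3. Test each contrast on its own variance, and name in advance a simpler fallback for non-convergence that does the same.
4. Keep the planned Greenhouse-Geisser ANOVA as the all-visit test, stating that it uses completers.
5. Report the number contributing at each visit for each outcome. If attendance was complete, this settles the matter.

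**Cost.** SAP wording and standard software; no new data. The model relies on data being missing at random, recovers only part of the lost power under permanent dropout, and loses a side difference when one eye is not measured. Its fit to coarse ordinal grades is untested, and small samples are a risk: with 10% of each later visit skipped, non-convergence was 1 in 1200 at n = 30 and 17 in 1200 at n = 20. The plan is written in the past tense; if the data have already been analysed, the model must be labelled post hoc.

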## Background and purpose

As the mechanisms of action underlying commonly prescribed light-based therapies are still not fully understood, our study aims to investigate clinical and physiological changes on the surface of the eyes and eyelids using clinically and readily available instruments. Two light-based therapies commonly prescribed are intense pulsed light (IPL) and low-level light therapy (LLLT), often in combination (IPL+LLLT). While IPL+LLLT is becoming a more common treatment regimen worldwide, recent evidence has also shown that LLLT alone is more effective at alleviating dry eye signs and symptoms better than IPL (Giannaccare et al, 2023). The proposed study aims to investigate the short- and long-term morphological, functional and physiological changes in the eyelid skin and ocular surface following IPL+LLLT versus LLLT alone (with prior sham IPL) for the treatment of Meibomian gland dysfunction in dry eye disease. The findings from this study will contribute knowledge to eyecare practitioners regarding the cellular and molecular changes these treatments and strengthen clinical guidelines associated with the prescription of light-based therapies. Understanding the short- and long-term implications of these treatments will also enable eyecare practitioners to treat patients with a more evidence-based approach.

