**ii. Visual acuity assessment**

A standard vision chart mounted on the wall was used to assess high-contrast vision in logMAR units, calibrated at 3 m.

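### Should visual acuity be analysed in the two-factor treatment-by-visit model rather than in a time-only ANOVA?

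*Combined protocol and SAP*

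**What the plan says.** The Background and purpose section sets a comparative aim: changes "following IPL+LLLT versus LLLT alone (with prior sham IPL) for the treatment of Meibomian gland dysfunction". Figure 1 in the Light-based treatment protocol section makes the comparison within the person, with "sham IPL placement of a disconnected empty cartridge along the same five different regions on the contralateral side".

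The Statistical Analysis section then gives three procedures:

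- A comparative model over visits: "Two-factor repeated measures analysis of variance (ANOVA) was used for statistical analysis to assess changes over time across the multiple visits between each treatment group". No outcomes are named.
- A time-only model: "One-way repeated measures ANOVA was used to assess changes over time for overall measures including OSDI scores, DEQ-5 scores, visual acuity, and blink rate".
- A paired t-test or Wilcoxon signed-rank test, which "was used to assess differences between the two treatment modalities within the same visit". Again no outcomes are named.

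On measurement, the acuity section says: "A standard vision chart mounted on the wall was used to assess high-contrast vision in logMAR units, calibrated at 3 m". It does not say whether the eyes were tested separately or together. Table 2 has a row for "Visual acuity assessment" ticked at all six visits.

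**The concern.** In a contralateral design the treatment effect lies in the difference between the two sides. A one-way repeated measures ANOVA over visits has neither a treatment term nor a treatment-by-visit term. If acuity was measured in each eye and then reduced to one value per visit, the between-eye information is discarded. A change in vision could not then be attributed to IPL+LLLT, to LLLT alone, or to both.

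The paired test does not fully cover this. It compares levels at one visit and does not test the difference in change from Visit 1. The plan already contains a model that could carry the comparison, so naming acuity under the weaker one looks like an avoidable loss. At stake would be the trial's between-treatment statement on vision.

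**Working it through.** The document states no sample size, SD, alpha or effect size, so there is no planned figure to reproduce. The check has a textual part and an algebraic part.

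**1. What unit does the text imply for acuity?**

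| Measure | Where | Unit stated? | In the one-way list? |
|---|---|---|---|
| OSDI, DEQ-5 | Questionnaire section | Described per participant | Yes |
| Adapted SANDE | Same section | Yes, separately for each eye | Not named |
| Blink count | Keratograph Part 1 | Not stated | Yes (as blink rate) |
| Tear meniscus height, break-up time | Keratograph Part 1 | Not stated | Not named |
| Eyelid blood flow | Laser Doppler section | Yes, each side | Not named |
| Visual acuity | Acuity section | Not stated | Yes |

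The sorting follows the unit of measurement, not the instrument. SANDE is collected with OSDI and DEQ-5 but is not named with them. Blink rate comes from the same device as tear meniscus height but is separated from it. The named measures are those the authors call overall. Acuity in that company suggests one value per person. This is inference: the list opens with *including*, so it need not be complete.

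**2. If there is one value per person per visit.** There are 6 readings per participant and 6 − 1 = 5 within-person degrees of freedom, all for visit. The one-way model uses them all. No treatment contrast can be formed, so nothing is lost.

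**3. If there is one value per eye per visit.** There are 2 × 6 = 12 readings, equivalent to 6 two-eye means and 6 between-eye differences. The two-factor model has treatment 1 df, visit 5 df and treatment × visit 5 df. A one-way analysis of the means keeps only the 5 df for visit.

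Let a be the change in the IPL eye and b the change in the sham eye (logMAR, positive = loss; values are illustrations). The mean change is (a + b)/2 and the difference in change is a − b.

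- a = 0.10, b = 0: mean 0.05, difference +0.10
- a = 0.05, b = 0.05: mean 0.05, difference 0
- a = 0, b = 0.10: mean 0.05, difference −0.10

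One mean fits three different treatment effects. That holds as algebra, but averaging the eyes is itself an assumption; the document does not mention it for acuity.

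**4. The paired test (IPL/sham values, illustrative).**

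- Visit 1 0.00/0.10, Visit 6 0.10/0.10: Visit 6 difference 0, difference in change (0.10 − 0.00) − (0.10 − 0.10) = +0.10.
- Visit 1 0.10/0.00, Visit 6 0.10/0.00: Visit 6 difference 0.10, difference in change 0.

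Both cases need a 0.10 imbalance at Visit 1. A paired test at Visit 1 bears directly on that, although it is not a formal test of change.

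**5. What the two-factor run would add.** With two treatments within the person, the treatment × visit test is a one-way repeated measures ANOVA on the between-eye difference. In a two-visit numerical check the interaction F equalled the squared paired t (5.2265). Over six visits it is an omnibus test on 5 df and gives no single estimate until a contrast between two visits is named.

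Under assumed values (SD 0.10 logMAR, between-visit correlation 0.7, between-eye correlation r, n participants), the standard error of such a contrast is 0.10 × √[4(1 − 0.7)(1 − r)/n]. For n = 30 and r = 0.6 this is 0.10 × √(0.48/30) = 0.0126, a 95% half-width of 0.026. Over n = 20 to 40 and r = 0.3 to 0.8 the half-width runs from 0.043 down to 0.016.

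A simulation on the same assumptions, with a 0.05 difference in change, had the time-only test rejecting in about 3–5% of runs and the interaction in about 59–100%. It fixed the two-eye mean change at zero, so the time-only test could reject only at about its null rate. That contrast is built in and says nothing about importance in this trial.

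**The case for a change.** The best case for acting is that it costs almost nothing under either reading. With per-eye data, one further run of a model already in the plan gives the comparison the design was built for. With binocular data, one sentence in the report would prevent an over-reading. The acuity section's silence is also weak evidence of binocular testing: the Keratograph section does not state the eye either, for measures such as tear meniscus height that belong to a single eye.

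Part of this stands. The recording unit is not stated, a time-only model carries no treatment information, and a within-visit test is not a test of change. Silence in the acuity section should carry little weight by itself; the overall label and the company acuity keeps carry more.

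The rest is weaker. Nothing restricts acuity to the one-way model, because the two-factor and paired-test sentences name no outcomes. An analyst with per-eye values could use both within the plan as written. The two-factor run would also not deliver an estimate by itself; a target visit would have to be named.

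**Conclusion.** No change to the plan follows. On the more natural reading, acuity is one value per person per visit, the one-way model is the right fit, and the proposed alternative cannot be run. On the other reading, the plan already holds a two-factor model that does not exclude acuity, and the unstated unit is a detail the analysts would know from the data.

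The consequence is small either way. The stated aim concerns the eyelid skin and ocular surface, and no section marks acuity as a primary, key or safety outcome. The one-way result is also a fair description in its own right, since both sides receive LLLT and a shared change is plausible.

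This rests on reading *overall* as one value per person, which the text supports but does not prove. If acuity was binocular, it supports no between-treatment conclusion on vision, and the time-only model does not claim one. No trial-specific size can be given; every logMAR figure above is an illustration or an assumption.
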